4. STATISTICAL ANALYSES

The objectives of this enabling study are to characterise the wheal and flare responses over time following skin challenges with ascending concentrations of SP.

4.1. General Considerations

4.1.1. General Methodology

Unless otherwise specified, continuous data will be summarized using descriptive statistics: n, mean, standard deviation (SD), median, interquartile range, minimum and maximum. Categorical data will be summarized as the number and percentage of participants in each category.

4.1.1.1. Bayesian Inference

All the main statistical analyses will be carried out in the Bayesian framework. Models will be fitted by MCMC simulations. Vague priors will be used for modelling parameters and will be specified in the following sections. Sensitivity analyses on priors may be performed. Covariance structures may also be investigated..

The following summaries of the posterior distribution will be reported: posterior median, posterior standard deviation (SD), 95% equal-tailed credible interval (95% CrI), posterior probabilities of the true difference being greater than pre-specified thresholds.

The inference will be carried out as follows:

- 2 chains will be run, with different (over-dispersed) initial values in order to assess convergence. The posterior summaries will use only 1 chain.
- A minimum burn-in period of 10,000 MCMC samples (for each chain) will be used.

- A minimum of 10,000 MCMC samples (for each chain) will be run to generate samples of the posterior distribution.
- A thinning sample may be used to improve convergence. If k is the thinning ratio, the number of MCMC samples will be minimum $k*10,000$.

To assess convergence (MCMC), the following will be used:

- Ratio Monte Carlo error /posterior SD should be as small as to ensure that only a fraction of the posterior variability is due to simulation error.
The final MCMC samples will be such that this ratio for all the parameters in the model is ≤ 0.01 .
- Gelman & Rubin diagnostic is based on the ratio of the pooled variance across the chains over the overall within-chain variance. Values close to 1 indicate that each of the subsets of MCMC samples is close to the target posterior distribution.
A cut-off of 1.1 will be used.
- Diagnostic plots and visual inspection
 - o Trace plots (the distribution of points should not change as the chain progresses and the posterior mean and variance are relatively constant)
 - o Autocorrelation plots (provide information on how slow or fast the Markov chain converges)

To assess the model adequacy, diagnostic plots of the median predicted value vs median residual (should not show evidence of any patterns) will be used.

All the diagnostic outputs and alternative models fitted (where applicable) will be stored in the refdata folder in HARP (production) in the relevant reporting efforts.

4.1.2. Baseline Definition

For part 1, there will be 1 baseline value (baseline visit 1). For part 2, there will be 2 baseline values, one for each visit (baseline visit 1 and visit 2).

For the PD endpoints (wheal and flare responses), the baseline value will be the saline control non-missing value pre-SP challenge at challenge visit 1 and challenge visit 2 (parts 1 and 2). No missing baseline values will be allowed as part of the inclusion/exclusion criteria.

For the other endpoints collected at challenge visits 1 and 2, the baseline value will be the latest non-missing pre-1st control challenge assessment value at challenge visit 1 and challenge visit 2 (parts 1 and 2), including those from unscheduled visits.

For Part 2, the Baseline for Visit 2 will be the latest assessment performed after Visit 1 visits (such as Unscheduled) but before the first Visit 2 challenge.

Participants with a missing baseline value will be excluded from the change from baseline analyses.

The mean of replicate assessments at any given time point will be used as the value for that time point.

If baseline data are missing no derivation will be performed and baseline will be set to missing.

4.2. Primary Pharmacodynamic Analyses

4.2.1. Definition of endpoint

For parts 1 and 2, the primary endpoint is the wheal response-time area under the curve (AUC) over the 2h post-challenge period following skin challenge with ascending concentrations of SP on a single day (challenge visit 1) and 2 days (challenge visits 1 and 2), respectively, expressed as mm^2/min (see OPS).

The wheal response variable will be the area in millimetres squared (mm^2) and will be calculated using the following formula for area of an ellipse (see OPS), using the longest and orthogonal diameters measured by the calliper method.

The wheal response variable will be calculated for each ascending SP concentration and each control challenge (saline and histamine) and at each timepoint during the 2h post-challenge period at challenge visit 1 (parts 1 and 2) and challenge visit 2 (part 2).

The same as above will be repeated for flare.

4.2.2. Main analytical approach

4.2.2.1. Summary Measure

The summary measure is the difference in wheal response AUC between 2 consecutive SP concentrations at challenge visit 1 (parts 1 and 2) and at challenge visit 2 (part 2).

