### 2.2. Background

SP is a neuropeptide with an important role in neurogenic inflammation [Mashaghi, 2016]. When it is injected intradermally it causes wheal and flare responses, which increase in size with increased concentrations of SP [Borici-Mazi, 1999; Grouzmann, 2011; Sabroe, 1997; Zirbs, 2013]. While wheal and flare response to SP has been previously studied, the methods used to determine effect size differ between published reports and variability is difficult to establish. In addition, previous studies did not investigate possible modulation of pro-inflammatory markers and immune cells within the skin following SP challenge. This knowledge will aid the understanding of the mechanistic pathways downstream of SP activation.

Techniques such as intradermal microdialysis (IDM) can be used to take samples of interstitial fluid [Holmgaard, 2012; Baumann, 2019]. IDM involves insertion of dialysis membranes into the dermis, which is then perfused at a low speed with a physiological solution (the perfusate). Endogenous or exogenous molecules soluble in the extracellular fluid diffuse into the membrane and are collected in small vials for analysis. The technique has not previously been used to take samples from SP challenged skin.

This will be a 2-part study: Part 1 will aid understanding of the wheal and flare responses following intradermal SP Part 2 will investigate the variability of the responses, including the release of locally acting mediators and may include immune cells markers that can be detected in the skin after challenge..

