## 3. OBJECTIVES AND ENDPOINTS

### Part 1

Objectives	Endpoints
Primary	

To characterise the wheal response over time following skin challenge with ascending concentrations of SP on a single day

	

Wheal response during the 2 h post-challenge period area under the curve (AUC) at each concentration of SP

Secondary	

To characterise the wheal response over time following skin challenge with ascending concentrations of SP on a single day

	

Wheal response during the 2 h post-challenge period at each concentration of SP (including maximum observed wheal response, time to maximum observed wheal response, time of complete wheal response disappearance)

 
To characterise the flare response over time following skin challenge with ascending concentrations of SP on a single day
 
	
 
Flare response during the 2 h post-challenge period at each concentration of SP (including AUC, maximum observed flare response, time to maximum observed flare response, time of complete flare response disappearance)
 

 
To evaluate the safety and tolerability of SP
 
	
 
Incidence of Adverse Events (AE) and Serious Adverse Events (SAE)
 
Incidence of findings of clinical important changes in: 
 
vital signs
 
laboratory safety data
 
12-lead electrocardiogram (ECG)
 
 
 

## Part 2

Objectives	Endpoints
Primary	

 
To compare the wheal response over time following skin challenge with ascending concentrations of SP on two days
 
	
 
Wheal response during the 2 h post-challenge period (AUC) at each concentration of SP across 2 challenge days
 

Secondary	

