## **4.2. Scientific Rationale for Study Design**

The primary endpoint in this study is the wheal response, which directly links SP to inflammation. The wheal response is caused by accumulation of mast cell proteins in the dermis and presents as a raised oedema [Takahashi, 2004]. Flare, a secondary effect of degranulation, will also be measured. Mast cell degranulation stimulates neuropeptide release from neurons, which in turn causes superficial vasodilation presenting as a flare response, characterised by a reddened area of skin [Schmelz, 2000].

Exploratory biomarkers of mast cell activation and the resulting immune response may be measured, at the site of SP challenge and systemically, to aid understanding of the wheal and flare responses.

Wheal and flare responses to intradermal SP challenge peak and resolve over about 2 h in healthy people [Borici-Mazi, 1999]. Therefore, a 2 h sampling window following challenge is deemed appropriate. If review of wheal response data from Part 1 indicate that a longer or shorter sampling window is more appropriate, the sampling window will be changed accordingly; the maximum post challenge- sampling window will be 4 h.

It is unknown whether SP responses could change upon repeated challenge – e.g. because of exhaustion of mast cells. Timing of challenge days in Part 2 of this study will be chosen to evaluate anticipated intervals between challenge days in subsequent studies of antagonists.

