#### **4.3. Justification for Substance P concentrations**

Published data indicate that the wheal and flare responses to intradermal SP continue to increase with increasing concentrations, even up to 100  $\mu\text{mol/L}$  [Zirbs, 2013]. However, at the cellular level in an in-vitro mast cell line, SP begins to exert effects at  $\sim 0.1 \mu\text{mol/L}$  and the effect plateaus at  $\sim 10 \mu\text{mol/L}$ . The probable reason for the result in human skin is as the concentration of SP increases, it diffuses to a larger area of the dermis, causing larger reactions by activating more mast cells. To avoid concentrations of SP that are well above maximum effectiveness, the human mast cell line data were used to determine the SP concentrations in this study. Concentrations of 0.1, 0.3, 1 and 3  $\mu\text{mol/L}$  SP are expected to give a range up to  $\sim 95\%$  of the maximum effect at the cellular level. Those concentrations have been shown to cause wheal and flare responses when given intradermally to healthy people [Borici-Mazi, 1999; Grouzmann, 2011; Sabroe, 1997; Zirbs, 2013].

To allow for possible differences between published data and our SP challenge model, the concentrations of SP may be changed during the study in order to elicit the desired wheal response. For example, if the wheal response following one or more SP concentrations was indistinguishable from the wheal response following saline, and/or the wheal response was indistinguishable between 2 concentrations of SP, the concentrations could be adjusted accordingly. The maximum amount of SP administered in a single injection will not exceed 50  $\mu\text{L}$  of 10  $\mu\text{mol/L}$ .

The SP concentrations administered in Part 2 will be selected to ensure that the lowest concentration gives a wheal response larger than the wheal response following saline, and that each increasing concentration gives a wheal response larger than that at the previous concentration.

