### 9.4.1. General Considerations

This is an exploratory enabling study which is primarily designed to define the relationship between SP concentrations and wheal and flare response, within a range of intradermal SP concentrations. There are no formal hypotheses to be tested.

All the statistical analyses will be carried out in the Bayesian framework. Models will be fitted by Markov chain Monte Carlo simulations. The following summaries of the posterior distribution will be reported: posterior mean, posterior standard deviation (SD), posterior median, 95% equal tailed credible interval, posterior probabilities of the true effect being greater than pre-specified thresholds. Vague prior distributions will be used.

For all endpoints, the baseline value will be the negative control value. No missing baseline will be allowed (as part of the inclusion/exclusion criteria).

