Predictors (X)	
 SP = SP concentration (categorical) Visit = challenge visit (categorical) SP*visit = SP by-visit interactions (categorical) Saline_AUC_base = average baseline defined as the mean of the 2 saline-induced AUCs for each participant (continuous) Saline_AUC_visit = Deviation of each visit saline-induced baseline from average baseline defined as saline-induced AUC - Saline_AUC_base Saline_AUC_visit*visit = Saline_AUC_visit by-visit interactions
Subject-level effects (γ)	
 Z_i = design matrix for the subject-level effects $\gamma \sim Normal(0, \sigma^2 I)$
Model Checking & Diagnostics	
See Section 4.1.1.1	
Model Results Presentation	

 Summaries of the posterior distributions of true AUC for each SP challenge and the true difference in AUC using the mean baseline to calculate the marginal estimates Probabilities that the true difference in AUC is greater than 0 	

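### Part 2's primary question, the change in wheal response between two challenge days, has no named estimate or interval, and neither has SP minus saline

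*SAP*

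**What the plan says.** **Objective.** The Part 2 primary objective, in protocol section 3 and repeated in SAP 1.1, is "To compare the wheal response over time following skin challenge with ascending concentrations of SP on two days". Protocol 4.2 gives the reason: "It is unknown whether SP responses could change upon repeated challenge". It adds that the spacing of challenge days will be "chosen to evaluate anticipated intervals between challenge days in subsequent studies of antagonists". Protocol 2.2 says that "Part 2 will investigate the variability of the responses", and protocol 4.1 makes understanding of that variability the purpose of the data review at about 10 Part 2 participants.

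**Summary measure.** SAP 4.2.2.1 says: "The summary measure is the difference in wheal response AUC between 2 consecutive SP concentrations at challenge visit 1", and applies the same measure at visit 2. SAP 4.3.2.1 repeats it for flare.

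**Model and outputs.** The Part 2 model in SAP 4.2.2.2 contains SP concentration, visit, their interaction and saline covariates. Its results list gives posterior AUCs per SP challenge, an AUC difference that is not specified further, and the probability that this difference exceeds zero. The Part 1 results list, which has a single visit, uses the same words. SAP 4.1.1.1 attaches a 95% credible interval to posterior summaries in general.

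**Variability.** SAP 4.2.3 mentions a within-participant SD only for prior sensitivity. SAP Table 1 lists statistical analyses for review 2 without saying which.

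**Saline.** Protocol 9.4.2 says the primary analysis will assess AUC differences between challenges and names both saline and SP. The SAP summarises saline AUC descriptively and enters it as a covariate. SAP 4.8 records no change from the protocol.

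**The concern.** The consecutive differences have a proper use. Protocol 4.3 wants concentrations such that "each increasing concentration gives a wheal response larger than that at the previous concentration", and protocol 9.4.1 calls the study "primarily designed to define the relationship between SP concentrations and wheal and flare response". They should stay. But they are all taken within a visit, so they describe the shape of the concentration response on each day and not whether the response has moved between days.

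Part 2 brings participants back to find out whether the response moves. If mast cells are exhausted by the first challenge, or if the model is simply noisy from day to day, the sponsor needs the size of the change and its uncertainty before planning antagonist studies on the same interval. As written, a reader would have to judge this from two by-visit posteriors, which loses the within-participant pairing. The review at about 10 participants would also decide whether variability is understood without a named measure of it.

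**Working it through.** The plan states no effect size, SD, correlation or power, so there is no figure of its own to reproduce. All AUCs, SDs, slopes and correlations below are assumptions.

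**1. Can the named differences yield the day difference?** Four concentrations and two visits give 3 × 2 = 6 named differences, of rank 6. Adding any one of the four visit 2 minus visit 1 differences raises the rank to 7, so none can be built from the named set. The same holds for all eight SP-minus-saline differences.

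**2. Illustration.** Assume visit 1 AUCs of 1000, 2000, 3000 and 4000.

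| Change at visit 2 | Visit 2 AUCs | Consecutive differences | Day differences |
|---|---|---|---|
| Additive, −400 | 600, 1600, 2600, 3600 | 1000, 1000, 1000 | −400 at each |
| Proportional, −20% | 800, 1600, 2400, 3200 | 800, 800, 800 | −200, −400, −600, −800 |

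The additive shift is invisible in the named measure. The proportional one shows only indirectly, as 1000 becoming 800.

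**3. The reported probability.** Take P(difference > 0) as the t distribution function at d / (SD·√(2/n)) with n − 1 degrees of freedom, using the same SD between sites and between days. At n = 10:

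| SD | d = 1000 | d = 800 |
|---|---|---|
| 150 | 1.000 | 1.000 |
| 300 | 0.99998 | 0.99989 |
| 600 | 0.9976 | 0.9923 |

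This output hardly separates the days even under the proportional fall.

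**4. What a named day difference would give.** The half-width of the paired interval is t(0.975, n−1)·SD·√(2/n), close to a vague-prior credible interval without covariates.

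| SD | n = 10 | n = 20 |
|---|---|---|
| 150 | 152 | 99 |
| 300 | 304 | 199 |
| 600 | 607 | 397 |

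At SD 300 and n = 10, the additive change is −400 ± 304 and the proportional change at the top concentration is −800 ± 304. At the lowest concentration the proportional change is −200 ± 304, which includes zero. At SD 600 and n = 10, −400 ± 607 also includes zero.

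**5. Loss of pairing.** For equal variances, the independent-visit interval is wider than the paired one by √2 / √(2(1−ρ)) = 1/√(1−ρ). At ρ = 0.3, 0.5, 0.7 and 0.8 this is 1.20, 1.41, 1.83 and 2.24. Simulation with 20,000 trials of n = 20 gave 1.195, 1.415, 1.826 and 2.237.

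**6. Effect of the saline adjustment.** Suppose SP falls by 400 in total and saline by 100, so the saline deviations from the participant mean are +50 and −50. With common slope b, the day difference at zero deviation is −400 + 100b: −350, −300 and −200 for b = 0.5, 1 and 2. The unadjusted paired difference stays at −400. The two answer different questions, so both are needed.

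**7. Within-participant SD.** A model-based value would be √((Σ11 + Σ22 − 2Σ12)/2). With Σ11 = Σ22 = 300² and Σ12 = 0.2·300², this is √72,000 = 268.3. It equals the SD of paired differences over √2 only if the subject-level effect γ is a participant intercept. If γ also contains a participant-by-visit effect with SD 100, 200 or 300, the paired value (400,000 simulated draws) is 286.8, 334.6 or 402.7. The SAP does not say what γ is.

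**The case against.** The study is exploratory, tests no hypothesis and sizes nothing on this contrast. The Part 2 model already has visit and interaction terms, the SAP sets 95% credible intervals for posterior summaries, and participant data can be listed, so the day difference can be recovered. The AUC difference in the Part 2 results is not defined where it appears, and detailed output rules sit in the programming specification (OPS), which is not public. On saline, protocol 9.4.1 makes the negative control the baseline, 9.4.2 permits baseline adjustment and other approaches, and SAP 4.1.2 mentions change-from-baseline analyses, so a covariate role is arguably within the latitude given. The illustration rests on assumed values, the probability of a positive step was never meant to compare days, and at small n or large SD the day interval would be wide anyway.

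Much of this stands as a limit on severity. Nothing is lost that cannot be computed, and the posterior median and interval of each step would show 1000 falling to 800. It does not supply the missing estimate. A model term is not an output, and the general interval rule covers only quantities that are reported. SAP 4.2.2.1 is the only visible definition of the difference, and the same results wording serves Part 1, where no day contrast exists. The SAP says its purpose is to describe planned analyses and output, so the primary contrast belongs there. A wide interval would itself be informative. On saline, the model choice is optional in protocol 9.4.2, but the assessment of differences between saline and SP is stated as something that will be done.

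**Conclusion.** The concern holds. As written, the SAP names no estimate or interval for Part 2's primary question, and an additive day shift cancels from every difference it does name. This should be fixed, but it threatens neither error rates nor data. The cancellation is exact and needs no assumption. The other sizes (day intervals of about ± 152 to ± 607 at n = 10, and intervals 1.20 to 2.24 times too wide when pairing is ignored) depend on assumed SDs of 150 to 600 and correlations of 0.3 to 0.8. The unnamed within-participant SD and the undeclared omission of SP minus saline are lesser parts of the same gap.

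**What to change.** 1. In SAP 4.2.2.1, SAP 4.3.2.1 and the Part 2 results presentation, add the visit 2 minus visit 1 difference in AUC at each SP concentration, with its 95% credible interval. For wheal, make it a primary Part 2 summary measure alongside the consecutive differences. Evaluate it at a saline deviation of zero (Saline_AUC_visit = 0) and report the unadjusted paired difference beside it, because the adjustment can absorb a shift shared with saline.
2. Name the between-day within-participant SD as an output and supply it to the review at about 10 participants. Take it per concentration as the SD of the unadjusted paired differences divided by √2. Give a model-based version only after the SAP states what γ represents.
3. Either add the paired SP-minus-saline AUC difference with its interval, or record the departure from protocol 9.4.2 in SAP 4.8. Saline is not a response level in the model, so this would be a separate paired summary.

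The cost is SAP wording, contrasts from MCMC samples already planned, and simple paired summaries. Item 3 can be one sentence. No new data are needed and the Part 2 model does not change.

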### **6.1. Study Intervention(s) Administered**

Participants will receive saline and SP by intradermal injection, and histamine by skin prick.

Saline and histamine will be sourced by the site; histamine will be administered in accordance with manufacturer's instructions.

SP drug substance will be supplied by GSK and prepared into drug product extemporaneously at the trial site prior to administration.

Intervention Name	Substance P
Type	Drug
Formulation	Solution for injection
Unit Strength(s)	3.0, 1.0, 0.3 and 0.1 $\mu$ mol/L (with possible increase up to 10 $\mu$ mol/L, if no wheal and flare response is observed)
Dosage Level(s)	50 $\mu$ L of: 150, 50, 15 and 5 pmol (with possible increase up to 500 pmol if no wheal and flare response is observed)
Route of Administration	Intradermal injection
Use	Challenge agent
Sourcing	Drug substance provided centrally by sponsor then prepared to drug product locally by the trial site.
Packaging and Labelling	Study Intervention will be provided in vials. Each vial will be labelled as required per country requirement.

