### **6.5. Modification of Substance P concentrations**

Following data reviews at the data review committee (DRC) (see Section [10.1.5](#)) in Part 1, higher/lower concentrations of SP might be administered to subsequent participants, depending on the wheal reactions observed (see Section [4.3](#)). The maximum amount of SP administered in a single injection will not exceed 50  $\mu$ L of 10  $\mu$ mol/L, and up to a maximum of 10 injections of SP will be allowed per challenge visit.

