## 9.5. Interim Analyses

No formal interim analysis will be performed. The following data monitoring will be performed based on data collected during the study. At a minimum, all reviews will include available wheal response data after each injection of SP.

- Part 1 data for about 3 participants who have completed the challenge visit will be reviewed prior to enrolment of subsequent participants, to allow any concentration adjustment.
- Part 1 data for about 6 participants who have completed the challenge visit will be reviewed prior to enrolment of subsequent participants, to allow any concentration adjustment and/or to confirm if sufficient data is already available to progress to Part 2.
- Part 1 data will be reviewed prior to participants being enrolled into Part 2.
- Part 2 data for about 10 participants who have completed the 2 challenge visits will be reviewed; enrolment into Part 2 may continue during the review.

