4.2.2.2. Population of interest

The primary pharmacodynamics analyses will be based on the Safety population and on participants who have completed the challenge visits (complete case analysis).

Statistical analyses

Unless otherwise specified, endpoints / variables defined in Section 4.2.1 will be summarised using descriptive statistics, graphically presented and listed (where appropriate).

Statistical Methodology Specification for Part 1

Endpoint / Variables	

 SP-induced wheal response-time AUC at challenge visit 1 	
Model Specification	

 Bayesian analysis of covariance (ANCOVA) 	
Model	$y_i \sim Normal(\mu_i, \sigma)$ $\mu_i = \mathbf{X}_i \boldsymbol{\beta}$
Response	y_i = AUC for participant i
Prior for σ	σ = between-participant SD $\sim Gamma$ (shape = 2, rate = $\frac{1}{A}$) with A reasonably large e.g. A=10 (Chung et al, 2013)
Population-level coefficients ($\boldsymbol{\beta}$)	$\boldsymbol{\beta}$ = parameters associated to predictors $\beta_k \sim Normal(0, sd = 1e6)$
Predictors (\mathbf{X})	
 SP = SP concentration (categorical) Saline-induced (Baseline) wheal response-time AUC (continuous)
Model Checking & Diagnostics	
See Section 4.1.1.1	
Model Results Presentation	

 Summaries of the posterior distributions of true AUC for each SP challenge and the true difference in AUC using the mean baseline to calculate the marginal estimates Probabilities that the true difference in AUC is greater than 0 	

Statistical Methodology Specification for Part 2

Endpoint / Variables	

 SP-induced wheal response-time AUC at challenge visits 1 and 2 (using only data when no IDM intervention was done) 	
Model Specification	

 Bayesian analysis of covariance (ANCOVA) with visit effects 	
Model	$\mathbf{Y} \sim MVN(\boldsymbol{\mu}, \boldsymbol{\Sigma})$ $\boldsymbol{\mu} = \mathbf{X}\boldsymbol{\beta} + \mathbf{Z}\boldsymbol{\gamma}$
Outcome	y_{ij} = SP-induced AUC for participant i at visit j

Prior for Σ (covariance matrix)	$\Sigma_{ij} = Cov[Y_i, Y_j]$ assumed to be unstructured $\Sigma \sim$ Inverse Wishart (J, R), with $J = 2$ (visits), R = empirical covariance matrix
Population-level coefficients (β)	β = parameters associated to predictors $\beta_k \sim Normal(0, sd = 1e6)$ β_0 = intercept, Vague: $Normal(0, sd = 1e6)$

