4.7. Data reviews

All data reviews will be performed by the data review committee (DRC) (see Section 10.1.5 of the protocol) in accordance to the Dose Escalation Plan and are summarised in

Table 1. Study population and safety data will be generated by the site, wheal and flare data will be generated by S&P.

Table 1 Timing, purpose, outcomes and data to be reviewed at each data review

Data review number	Timing	Purpose	Potential outcomes	Data to be reviewed
1.1	~3 participants who have completed the part 1 challenge visit	Review safety data Review PD data	Stop/pause study or recommend alterations to study design or conduct for safety Modify SP concentrations for the next participants to be enrolled in part 1 Continue recruitment to part 1 at the same SP concentrations	Study population Safety Wheal response (plots)
1.2	~6 participants who have completed the part 1 challenge visit	Review safety data Review PD data	Stop/pause study or recommend alterations to study design or conduct for safety Modify SP concentrations for the next participants to be enrolled in part 1 Stop recruitment to part 1 and open up part 2 Continue recruitment to	Study population Safety Wheal response (plots)

Data review number	Timing	Purpose	Potential outcomes	Data to be reviewed
			part 1 at the same SP concentrations	
1.3	~12 participants who have completed the part 1 challenge visit	Review safety data Review PD data	Stop/pause study or recommend alterations to study design or conduct for safety Confirm SP concentrations for part 2 Stop the study	Study population Safety Wheal response (plots, summary tables) Flare response (plots, summary tables)
2	~10 participants who have completed the part 2 challenge visit 2	Review safety data Review PD data	Stop/pause study or recommend alterations to study design or conduct for safety Continue recruitment to part 2 Stop the study	Study population Safety Wheal response (plots, summary tables, stats analyses) Histamine concentrations (plots, summary tables) if available

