5. SAMPLE SIZE DETERMINATION

A sufficient number of participants will be screened in order to enroll approximatively 32 participants in the study (up to 12 in part 1 and up to 20 in part 2). The sample size for part 1 and part 2 is not based on statistical considerations and is based on previous published data.

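### If concentrations change during Part 1, the SAP does not define a consecutive step, and its Part 1 model lets cohort differences into the affected steps

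*SAP*

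**What the plan says.** SAP 4.2.2.1 defines the primary measure: "The summary measure is the difference in wheal response AUC between 2 consecutive SP concentrations at challenge visit 1 (parts 1 and 2"). SAP 4.3.2.1 defines the flare measure in the same way.

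The concentrations are not fixed during Part 1. Protocol 6.5 says that "higher/lower concentrations of SP might be administered to subsequent participants, depending on the wheal reactions observed". Protocol 9.5 sets the first decision point: "Part 1 data for about 3 participants who have completed the challenge visit will be reviewed prior to enrolment of subsequent participants". A second review follows at about 6 completers. SAP 4.7, Table 1, lists this outcome for both reviews: "Modify SP concentrations for the next participants to be enrolled in part 1". The starting strengths in Protocol 6.1 are "3.0, 1.0, 0.3 and 0.1 $\mu$ mol/L (with possible increase up to 10 $\mu$ mol/L, if no wheal and flare response is observed").

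The Part 1 model in SAP 4.2.2.2 has two predictors: "SP = SP concentration (categorical") and the saline-induced AUC. It has no participant effect and no cohort term. The Part 2 model in the same section does have subject-level effects. Allocation is not randomised (SAP 1.2), so the order of enrolment decides who receives which set of concentrations. The planned size is "up to 12 in part 1 and up to 20 in part 2".

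**The concern.** While all Part 1 participants receive the same four concentrations, every step compares participants with themselves, and a generally reactive or unreactive person cancels out. After a change, the pooled list holds concentrations that only some participants received. A step next to such a concentration then compares partly, or wholly, different people, and the estimate contains the difference in skin reactivity between the early and later cohorts.

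Protocol 9.4.1 describes the study as "primarily designed to define the relationship between SP concentrations and wheal and flare response", and SAP 4.2.2.2 reports each difference with the probability that it exceeds 0. A step contaminated by cohort would be reported as an effect of concentration. The trigger for a change is the early cohort's own wheal reactions. If an upward move follows a chance run of weak responders, the cohort difference is not neutral noise.

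**Working it through.** **Inputs from the documents.** Up to 12 participants in Part 1; up to 4 concentrations each; possible change after about 3 or about 6 completers; categorical concentration; no participant term. The documents give no SD, within-participant correlation or target step size, so there is no figure of the plan's own to reproduce.

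**Assumptions.** Sigma is the SD between participants at one concentration. The within-participant correlation rho is 0.7, with 0.3 and 0.5 also shown. The saline covariate is left out, so the carried fractions are upper bounds. The shift patterns only illustrate structure and are not proposals about concentrations.

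**1. Fraction of a cohort difference carried, model as written.** Let D be the later cohort's mean responsiveness minus the early cohort's. Without a participant term, and ignoring saline, each concentration mean is the plain average of those who received it.

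One-level shift after 3 participants (lowest level dropped, one higher added; 3 then 9 participants):
- Lowest level: 3 early participants, mean shift 0.
- Levels received by everyone: (3 × 0 + 9 × D)/12 = 0.75 D.
- Added level: 9 later participants, D.
- First step: 0.75 D − 0 = **0.75 D**. Two middle steps: **0**. Last step: D − 0.75 D = **0.25 D**.

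The same shift after 6 gives 0.50 D for the first and last steps and 0 for the middle ones. If adjacent levels share no participants, the step carries **1.00 D** in size.

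By chance alone, D has an SD of sqrt(1/3 + 1/9) = 0.667 of the between-participant SD for 3 against 9, and sqrt(1/6 + 1/6) = 0.577 for 6 against 6.

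**2. Effect of a participant term** (random intercept, generalised least squares), one-level shift after 3:

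| rho | First step, fraction of D | Last step, fraction of D | First-step SE as written | First-step SE with participant term |
|---|---|---|---|---|
| 0.3 | 0.75 → 0.33 | 0.25 → 0.11 | 0.606 sigma | 0.570 sigma |
| 0.5 | 0.75 → 0.19 | 0.25 → 0.06 | 0.577 sigma | 0.489 sigma |
| 0.7 | 0.75 → 0.09 | 0.25 → 0.03 | 0.548 sigma | 0.383 sigma |

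The as-written SE at rho = 0.7 is sqrt(1/3 + 1/12 − 2 × 3 × 0.7/36) = sqrt(0.300) = 0.548 sigma. Pairing only the 3 shared participants gives sqrt(2 × 0.3/3) = 0.447 sigma, so the participant term does better than pairing alone.

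**3. No shared level, 3 then 9 participants.** A cross-cohort step has SE sqrt(1/3 + 1/9) = 0.667 sigma at any rho. A participant term leaves the carried fraction at 1.00. The steps that can be estimated within participants have SE sqrt(2(1 − rho)/n):

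| rho | n = 3 | n = 9 | 0.667 divided by each |
|---|---|---|---|
| 0.3 | 0.683 sigma | 0.394 sigma | 1.0 and 1.7 |
| 0.5 | 0.577 sigma | 0.333 sigma | 1.2 and 2.0 |
| 0.7 | 0.447 sigma | 0.258 sigma | 1.5 and 2.6 |

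**The case against.** **Consecutive may already mean within a participant.** Injections are given in ascending order at one visit, so the term can be read as adjacent steps in the sequence received. That is a fair reading, and SAP 4.2.2.1 does not say that pairs are formed across different sets of concentrations. But it does not exclude it, and the within-participant reading alone does not cure the pooled model: with a one-level shift after 3, the first step still contrasts 3 people with 12.

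**Full non-overlap is the extreme case.** Protocol 4.3 gives as examples a level indistinguishable from saline or two levels indistinguishable from each other. These suggest replacing or extending some levels and keeping others. This stands: a reader might infer that after any change every step compares different people, but steps between levels that everyone received stay clean.

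**Comparison with 12 participants.** A reader might set the cross-cohort SE against a within-participant step in all 12 (0.224 sigma at rho = 0.7) and conclude that precision is about three times worse. With no level shared, no 12-participant step exists. The fair comparators are 3 or 9 participants.

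**The uncertainty is shown and the stakes are limited.** For a fully cross-cohort step, the model's independent-error variance is the right one, so chance cohort differences are inside the credible interval. No hypotheses are tested. Part 1 reviews rely on plots, with summary tables only at the third, and Part 2 re-estimates the steps in up to 20 people with subject effects. All this stands and limits the harm. It does not make a cohort contrast a concentration effect, and tables pooled by concentration mix cohorts in the same way.

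**Saline AUC adjusts for reactivity.** It does so only partly. Participants must be saline-negative at screening (Protocol 5.1, criterion 3), so it may capture little of the response to SP; the documents give no figure.

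**Conclusion.** The point holds, conditionally and for Part 1 only. If the committee changes concentrations, the SAP leaves the primary step undefined, and its Part 1 model mixes cohort differences into the affected steps: 75% and 25% for a one-level shift after 3, 50% each after 6, and 100% where adjacent levels share nobody. These fractions follow from the participant counts and are upper bounds, because saline adjustment is ignored. The standard errors rest on the assumed correlation. At 0.7, a cross-cohort step is 1.5 and 2.6 times as noisy as the attainable within-participant steps; at 0.3 the first of these disadvantages vanishes.

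A reader might also infer that a participant effect never helps. That is true only where no participant received both levels; where levels are shared, it removes most of the carried difference at correlations of 0.5 and above. If no concentration is changed, the problem does not arise. The Dose Escalation Plan and the Output & Programming Specification were not available and might contain a handling rule, but the primary measure should be complete in the SAP itself.

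**What to change.** - In SAP 4.2.2.1 and 4.3.2.1, define a consecutive difference as one between adjacent concentrations received by the same participants at the same visit.
- In SAP 4.2.2.2, add a participant effect to the main Part 1 model, as Part 2 already has. It carries over to flare through SAP 4.3.2.3.
- For each step, report how many participants contribute to each concentration and how many received both.
- Where two concentrations share no participants, either do not report the difference as a concentration step or label it as a between-cohort comparison.
- Optionally, add a supplementary model with log concentration as a continuous term and a participant effect, to link the different sets. Its downside is an assumed log-linear shape, so it should stay supplementary.

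The cost is SAP wording, one added model term and two counts per step. No visit, concentration or sample size changes. The rule should be settled before the data are seen, so that the pairings are not chosen from the results.
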